Table 3. Schedule of investigations and outcome measures. Note: orange ticks indicate standard care.	33
Table 4. Justification of investigations and outcome measures	38
Table 5. COVID-19 contingency plan	46
Table 6. Feasibility outcome measures.....	48
Table 7. Standardised verbal communication during aerobic exercise.....	70

List of figures

Figure 1. Framework depicting key post-stroke phases and temporally related biological processes.	17
Figure 2. A bed-side power-assisted cycle ergometer (Medimotion, Letto 2).	19
Figure 3. Study flow chart.....	22
Figure 4. Pie charts displaying the risk of adverse events related to aerobic exercise.	32
Figure 5. Schematic diagram of 5-day exercise protocol.	52

i. Abbreviations

Abbreviation	Meaning
AE	Adverse event
ASU	Acute stroke unit
ATAS	Aerobic exercise training in acute ischaemic stroke
AWRC	Advanced Wellbeing Research Centre
BDNF	Brain-derived neurotrophic factor
BHRU	Beech Hill Rehabilitation Unit
CBF	Cerebral blood flow
CO ₂	Carbon dioxide
CPET	Cardiopulmonary exercise test
EQ-5D	EuroQol Quality of Life Index
FSS	Fatigue Severity Scale
GAD-7	Generalised Anxiety Disorder
GCP	Good Clinical Practice
GPAQ	Global Physical Activity Questionnaire
HASU	Hyper acute stroke unit
HR	Heart rate
HRmax	Maximum heart rate
HRR	Heart rate reserve
mBDNF	Mature brain-derived neurotrophic factor
MoCA	Montreal Cognitive Assessment
mRS	Modified Rankin Scale
NHS	National Health Service
NIHSS	National Institutes of Health Stroke Scale
PHQ-9	Patient Health Questionnaire
PI	Principal Investigator
PPI	Patient and public involvement
RCT	Randomised controlled trial
REC	Research Ethics Committee
RHH	Royal Hallamshire Hospital
rLOT	Revised Life Orientation Test
RoFS	Rating of Fatigue Scale
RPE	Rating of perceived exertion
SAE	Serious adverse event
SHU	Sheffield Hallam University
SPPB	Short physical performance battery
STH	Sheffield Teaching Hospitals
TMG	Trial Management Group
VO ₂	Oxygen consumption

ii. Trial summary

Trial title	Aerobic exercise training in acute ischaemic stroke: A single-centre, single-blinded, randomised, controlled feasibility study of an aerobic exercise training intervention versus standard care in the acute phase of stroke	
Internal ref. no. (or short title)	Aerobic Exercise Training in Acute Ischaemic Stroke (ATAS).	
Clinical phase	II	
Trial design	A single-centre, single-blinded, two-arm parallel group, randomised, controlled feasibility trial	
Trial participants	Acute ischaemic stroke patients (1-7 days post stroke)	
Planned sample size	30	
Intervention duration	5 working days	
Trial duration per participant	3 months	
Estimated total trial duration	21 months	
	Objectives	Outcome Measures
Primary	To determine the feasibility of conducting a randomised controlled trial (RCT) to assess the effects of an aerobic exercise intervention on stroke outcomes.	
 • safety • recruitment rate • exclusion rate • consent rate • dropout rate • participant fidelity to intervention • acceptability • completeness of data
Secondary	To identify potential primary outcomes for a subsequent definitive RCT.	
For example:
 
 • physical function/disability • health-related quality of life • cognitive function • mood • fatigue

	To develop mechanistic knowledge of the intervention.	
 physical activity levels Cerebral blood flow velocity Mature brain-derived neurotrophic factor
Type of intervention	Power-assisted aerobic exercise training.	
Intervention components	A 10-30 minute session of low-moderate aerobic interval exercise conducted once per day for 5 working days. Exercise type: semi-recumbent power-assisted in-bed cycling.	

iii. Funding and support in kind

Funder(s)	Financial and non-financial support given

Sheffield Hallam University
 
[contact]
 
Email: [contact]
	
Vice Chancellor's PhD Scholarship:
 
£15,009 per annum salary for PhD student for 3 years (£45,027)
 
£1,500 per academic year for research-related costs including consumables, patient transport and research dissemination (£4,500)
 
Total = £49527

Sheffield Teaching Hospitals NHS Foundation Trust, Department of Neurosciences.
 
[contact]
 
Email: [contact]
	
Transcranial Doppler ultrasound device provided in kind.
 
Cycle ergometer provided in kind.

iv. Role of Sponsor and Funder

We have facilitated three PPI events which were used to gather feedback from people affected by stroke, and healthcare practitioners. For the first two PPI events, the topic of interest was the acceptability of our proposed exercise protocol and overall research design. Adjustments to the research protocol have been made based on feedback from the events (see ATAS - Patient and Public Involvement. January 2020). In response to a suggestion at this PPI event, we created an aphasia-friendly participant information sheet (ATAS - Aphasia-Friendly Participant Information Sheet. Version 2. 25.08.2020) using the Stroke

Association guidelines for accessible information. This document has been reviewed by [name] (Speech and Language Therapist, and Patient and Public Involvement Research Coordinator for Integrated Stroke and Geriatric Medicine, Sheffield) who has stated that the document is well-designed and provides sufficient information for individuals with aphasia to make an informed decision.

In October 2020, we hosted an online PPI event which was attended by people affected by stroke and aphasia, and [name]. The purpose of this event was to review the style and content of visual aids that we intend to use to facilitate participant engagement in the research. These visual aids have been designed using the Stroke Association guidelines for accessible information. The PPI feedback was generally positive, and some minor amendments were made based on the PPI panel's suggestions (Aphasia-Friendly Visual Aids. V1 – 23.10.2020).

We will deliver a final PPI event after the data collection period. The purpose of this event is to seek the support of study participants and the wider stroke population to determine the most appropriate ways to translate and disseminate our findings to people affected by stroke. This will be held at a community venue with accessible parking and facilities for people with disabilities. Travel expenses will be paid to PPI participants for this event.

viii. Keywords

ATAS, acute ischaemic stroke, aerobic exercise, feasibility, stroke rehabilitation.

1. Main research question

Is a full-scale randomised controlled trial (RCT) (to test the hypothesis that aerobic exercise training initiated in the acute phase of stroke leads to better clinical outcomes compared to standard care) feasible?

2. Abstract

Ischaemic stroke is a leading cause of death and long-term disability which affects over 100,000 people per year in the UK. The condition involves the blockage of a cerebral blood vessel which restricts blood supply to part of the brain and results in brain tissue death.

Despite major advances in stroke care in recent decades, over half of stroke survivors suffer with a long-term disability and have a reduced quality of life. This poses a major burden on stroke survivors and their support network, as well as health and social care services. Early-initiated aerobic exercise training is a promising, novel intervention which may enhance recovery from stroke and thereby improve stroke survivors' level of independence and quality of life.

The purpose of this study is to determine whether it is feasible to conduct a RCT to test the hypothesis that aerobic exercise training initiated in the acute phase of ischaemic stroke (1-7 days post-stroke) results in better clinical outcomes than standard care alone. The proposed mode of aerobic exercise is power-assisted cycling which enables people with hemiplegia or hemiparesis to exercise whilst remaining in their hospital bed. The study will focus on feasibility outcomes including recruitment, safety and acceptability. Exploratory outcomes will also be measured to advance mechanistic knowledge of the intervention and to identify suitable outcome measures for a full-scale clinical trial.

3. Background

Stroke is the primary cause of long-term disability worldwide (1). It is estimated that 50-65% of stroke survivors live with a long-term disability or depend on a caregiver (2,3). The emotional impact of stroke is also profound, with approximately 30% of stroke survivors living with depression (4). The total economic burden of stroke in the UK is £26 billion per year, and this figure is estimated to rise to £75 billion over the next 20 years due to improvements in stroke survival rates and an ageing population (5). 85% of stroke events are diagnosed as ischaemic stroke (6) which is defined as an episode of neurological dysfunction lasting longer than 24 hours, attributed to vascular occlusion (7). Following ischaemic stroke, a complex cascade of pathological events occurs. Briefly, depleted energy stores lead to ionic imbalance, excitotoxicity, oxidative stress, inflammation, blood brain barrier dysfunction, oedema and ultimately, infarction of the cerebral parenchyma (8). The extent of cell death and stroke-induced disability is dependent on the volume, location and duration of cerebral ischaemia (9). Surrounding the infarct core is a region of hypoperfused but potentially salvageable tissue called the ischaemic penumbra which is estimated to be viable for 24-48 hours post-stroke (10). The fate of the ischaemic penumbra is dependent on the speed of reperfusion relative to stroke onset, and the residual blood flow supplied by collateral blood vessels (11-13). In addition, after the initial ischaemic insult, a delayed cascade of pathological events occurs including vasogenic oedema, inflammation and programmed cell death. These events may lead to secondary infarct expansion up until ~4

days post-stroke (14,15). Currently, there are no medical treatments that mitigate delayed lesion expansion (9,16–18). Available treatment options are limited to reperfusion therapy (intravenous thrombolysis or mechanical thrombectomy) which can only be administered during a short time window after stroke (19). Further, 90% of stroke patients do not receive reperfusion therapy due to arriving at hospital after the licensed treatment timeframe, contraindications (e.g. high risk of bleeding), or lack of service provision (re: thrombectomy) (20,21). In addition, reperfusion therapy is not always successful and can exacerbate inflammation and oedema, inducing secondary cell death and possibly haemorrhagic transformation (22,23). As the incidence of stroke continues to rise, there is an urgent need to develop innovative treatments that enhance brain repair processes post-stroke and thereby reduce stroke-induced disability. Emerging evidence suggests that aerobic exercise training initiated in the acute phase of stroke (1-7 days post-stroke) may enhance brain repair, mitigate neurological deficit and augment neuroplasticity. However, this line of evidence is limited to rodent models of stroke. Research is required to attempt to translate these promising findings to the clinical setting (24–27).

4. Rationale

4.1. Acute aerobic exercise: proposed mechanisms

Aerobic exercise induces a variety of neurovascular stimuli which interact with reparative processes post-stroke. Two important mediating factors are neurotrophin concentration and cerebral blood flow (CBF). Mature brain-derived neurotrophic factor (mBDNF) is a neurotrophin which promotes neural cell survival (i.e. neuroprotection), the growth of new neurons (i.e. neurogenesis) and structural and functional neural adaptations in response to injury and environmental stimuli (i.e. neuroplasticity) (28). mBDNF is produced and stored in central and peripheral tissues. Its production is increased in response to neurological injury, neuronal activity and aerobic exercise (29). At the onset of aerobic exercise, activated cerebral neurons rapidly depolarise and release mBDNF from synaptic terminals. After which, mBDNF may exert its positive effects on local neurovascular tissues (29). The heightened metabolic rate of active cerebral neurons requires an increased supply of oxygen and glucose. Local blood vessels respond to this metabolic perturbation by increasing CBF to active regions in a process known as neurovascular coupling (30). In addition, aerobic exercise increases the metabolic rate of skeletal muscles which increases carbon dioxide (CO₂) production, blood pressure and cardiac output. Collectively, these integrated mechanisms contribute to a 10-30% increase in CBF during moderate-intensity exercise (30). Interestingly, just 20 minutes of moderate-intensity aerobic exercise has been shown to

increase hippocampal blood flow by 10-12% for at least 65 minutes post-exercise in healthy individuals (31). The hippocampus plays a key role in the growth of new neurons, memory formation and learning (32). These processes are moderated by the binding of mBDNF to its receptor, tropomyosin-related kinase B, which is abundantly expressed in the hippocampus (33,34). Increased availability of mBDNF within the hippocampus in response to aerobic exercise may therefore promote neurological recovery. In addition, increased blood flow to metabolically active tissues exerts shear stress on the vascular endothelium (29).

Endothelial shear stress stimulates the bidirectional release of mBDNF from endothelial cells; mBDNF can be secreted into interstitial fluid via the basal membrane, where it may interact with astrocytes and neurons, or can be secreted from the luminal membrane into the blood (35). Platelets are the primary storage site of mBDNF in the blood, accounting for 99% of the blood-borne mBDNF pool (29,36). During aerobic exercise, sympathetic activation of the spleen leads to thrombocytosis which transiently augments the circulating pool of mBDNF (29,37).

In summary, during moderate-intensity aerobic exercise, interconnected central and peripheral stimuli lead to a heightened production, secretion and transport of mBDNF. Increased availability of mBDNF in the brain after stroke may enhance neurological recovery, particularly during the acute phase when reparative processes are upregulated.

4.2. Aerobic exercise training during acute stroke: pre-clinical evidence overview

The timing of aerobic exercise training initiation relative to stroke onset is an important variable. In the first 24 hours after stroke, most cell death and neurological deficit occurs. This critical period is known as the hyperacute phase (38). Pre-clinical evidence suggests that undertaking aerobic exercise training in the hyperacute phase of stroke amplifies cellular stress which exacerbates cerebral injury and neurological deficit (39–41). During the subsequent acute phase (1 to 7 days post-stroke), growth-promoting genes are spontaneously upregulated which elicit neurogenesis, axonal growth, dendritic branching and synaptogenesis (42,43). During this transient window of heightened neuroplasticity, the nervous system is highly amenable to environmental stimuli (e.g. rehabilitation). Delaying rehabilitation beyond this sensitive period (e.g. by 14 or 30 days) impairs functional recovery and blunts neural reorganisation (43).

[figure not shown]

Figure 1. Framework depicting key post-stroke phases and temporally related biological processes. Adapted from Bernhardt et al. (2017).

Pre-clinical studies demonstrate that aerobic exercise training initiated in the acute phase of stroke augments neuroplasticity, evidenced by enhanced structural reorganisation of neuronal networks (e.g. dendritic branching and synaptogenesis) and elevations in biomarkers of neuroplasticity such as mBDNF (25). In rodent models of ischaemic stroke, the optimal exercise parameters which promote neuroplasticity are: 30 minutes of moderate-intensity aerobic exercise per day, initiated 3 to 7 days post-stroke (25). In addition, aerobic exercise training initiated in the acute phase of stroke may induce neuroprotective effects. Aerobic exercise training interventions that start 24 to 48 hours after stroke have been shown to reduce biomarkers of inflammation, oxidative stress and cell death, promote angiogenesis and reduce lesion volume (24). Neuroprotective effects were most commonly found with interventions that started in the early acute phase (24 hours vs. 3 to 7 days) and were carried out at low to moderate intensity for 20 to 30 minutes (24). In light of the pre-clinical evidence, it is plausible that a training intervention consisting of a daily 20 to 30 minute bout of low- to moderate-intensity aerobic exercise for 5 days, initiated 1 to 7 days after stroke, may have neuroprotective and neuroplasticity-promoting effects in the clinical stroke population.

4.3. Aerobic exercise training during acute stroke: clinical evidence overview

To our knowledge, there is only one clinical study (44) that has investigated the use of aerobic exercise training initiated within the acute phase of stroke. The purpose of this study was to assess the feasibility of a task-specific walking exercise training programme, and to determine if participants could attain a sufficient exercise intensity to improve cardiorespiratory fitness. Of note, this study did not investigate mechanisms related to

neuroprotection or neuroplasticity. Strømmen et al., (44) recruited 20 acute stroke patients (41.5 ± 14 h post-stroke; mild to no disability) and implemented a 5-day intervention consisting of twice-daily 30-minute bouts of treadmill walking at a moderate exercise intensity (50% of heart rate reserve [HRR]) (45). Standing and sitting rest breaks were permitted as required. More than half of participants experienced at least 1 adverse event (AE) during exercise. Dizziness was the most frequent AE, occurring in 8.5% (19/224) of all exercise sessions, and 4 sessions ended prematurely due to dizziness. In addition, although not reported as an adverse event, 8 sessions were cancelled due to tiredness (5 participants) and 28 sessions finished early due to exhaustion (number of participants not reported). Lastly, the target exercise intensity was only attained in 31% of sessions, and 8 participants (40%) did not achieve the target exercise intensity in any exercise session. The authors attributed the low exercise intensity to lower limb motor deficit which limited step frequency. This suggests that walking may be an unsuitable mode of aerobic exercise training during the acute phase of stroke recovery. No serious adverse events (SAEs) (e.g. neurological deterioration) occurred in the 30-day follow-up period therefore the authors concluded that a 14.7% AE rate was acceptable (33 AEs in 224 exercise sessions). As this was a feasibility trial, clinical outcomes were not explored. The occurrence of dizziness suggests that frequent and prolonged upright standing and walking may induce orthostatic stress which could be detrimental, especially during the acute phase of stroke when blood-brain barrier function is impaired (46). Indeed, standing upright has been shown to reduce CBF velocity by 13% relative to a supine position in chronic stroke (47). The landmark international AVERT trial found that very early (first mobilisation at a median of 18.5 hours post-stroke) and more frequent (3 additional bouts per day) mobilisation (out-of-bed sitting, standing or walking) was associated with a poorer functional outcome at 3 months post-stroke compared to usual care (first mobilisation at a median of 22.4 hours post-stroke). The physiological mechanisms were not explored in the AVERT trial, but it is plausible that orthostatic stress was a contributing factor to the negative outcome (47,48).

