7.8. Randomisation

A web-based permuted block randomisation procedure (sealedenvelope.com) will be used to allocate participants into one of the study arms: 1) usual care alone; 2) aerobic exercise training plus usual care. Participants will be stratified using the National Institutes of Health Stroke Scale (NIHSS): mild to moderate (0-15) and moderate to severe (>15) measured after reperfusion therapy or at a similar timepoint if not eligible for reperfusion therapy. Block

sizes of either 4 or 6 will be randomly chosen and block size will be masked from research team members involved in patient-facing research activities. An independent research team member will be responsible for the block randomisation procedure. They will be notified via email with participant ID numbers and a corresponding NIHSS score using a remote web-based system. The independent research team member will publish the group allocation which will be remotely accessible only to authorised research team members.

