8.3. Safety of aerobic exercise

Low- to moderate-intensity aerobic exercise is considered to be safe for medically stable acute ischaemic stroke patients without contraindications (44,63). The only study which has conducted a moderate-intensity aerobic exercise training intervention (five days of twice-daily, 30-min bouts of moderate-intensity walking exercise) reported no SAEs but occasional dizziness (8.5%; 19/224 sessions) and exhaustion (44). Exhaustion is not classed as an AE but is an important outcome when considering exercise tolerability; 24 out of 224 (10.7%) exercise sessions ended early as a result of exhaustion (9/20 participants). In addition, Kramer et al., (64) investigated the energy cost of two different 6-minute fitness assessments in acute stroke patients (median 4 days post-stroke; mild to moderate stroke; n=21). Ambulatory participants (n=14) performed a 6-minute walk test, whereas non-ambulatory participants (n=7) completed a 6-minute sit-to-stand test. The median rating of perceived exertion (RPE) reported at the end of each test was 12/20 and 13/20 for the walk and sit-to-stand tests, respectively (both moderate intensity). No SAEs or AEs were reported, and only one participant was unable to complete the walk test due to fatigue. Furthermore, Johnson et al., (65) demonstrated the safety of a graded exercise test in acute

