and subacute stroke patients (n=28, days post-stroke: median = 9; range = 5-11), although the authors did not specify the proportion of participants that were in the acute (1-7 days post-stroke) or early subacute phase of stroke (7-30 days post-stroke). One of the exercise test termination criteria was reaching 85% of age-predicted maximum heart rate (HRmax), which is classed as vigorous exercise intensity (45). Over half of the participants exceeded this upper heart rate threshold and no SAEs or AEs were observed. Lastly, in our preliminary work (ESCAPE trial; STH20750), 4 acute stroke patients successfully completed a single 30-minute moderate-intensity exercise session (13/20 RPE) and there were no AEs or SAEs. Importantly, none of the aforementioned studies reported follow-up safety outcomes. **We can confirm that there have been no SAEs or AEs related to aerobic exercise in the 3 months following our investigation.** In summary, there have been approximately 276 reported bouts of aerobic exercise conducted in the acute phase of stroke, ranging from 6 to 30 minutes in duration and from moderate to vigorous intensity. No SAEs have been reported, whereas the AE rate ranged from 0-14.7% (mean 12%). The higher frequency of AEs appears to be related to high exercise volume and the mode of exercise training (e.g. treadmill exercise twice per day for 5 days).

In our proposed aerobic exercise training intervention, participants will exercise at a moderate intensity (40-59% HRR; 12-13/20 RPE). Moderate-intensity aerobic exercise elicits a transient increase in cerebral perfusion and neurotrophin concentration (39,59) which may contribute to improved recovery after stroke (24–26). Exercise duration will gradually increase from 10 minutes in the first session (day 1) to 30 minutes in the fifth session (day 5) (5-minute increment per day). Heart rate (HR) will be monitored continuously during exercise to ensure that moderate intensity is not exceeded. Heart rate reserve – the difference between resting HR and HRmax – represents the capacity for the HR to increase under stress. Measurement of HRmax is not appropriate due to the required vigorous exercise intensity. Instead, age-predicted HRmax will be calculated using the Inbar equation which estimates HRmax with greater accuracy than the commonly used formula of 220-age (66).

Inbar equation: $205.8 - (0.685 \times \text{age})$.

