8.4.1. Risk categorisation

Taking into account the absence of reported SAEs and our risk management procedures, we believe that this intervention is low risk. However, there is a lack of reported long-term follow-up outcomes. Due to this uncertainty, we propose that this intervention should be categorised as type B, that is, somewhat higher than the risk of standard medical care.

8.5. Risks and benefits to be communicated to patients (lay summary):

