8.5.2. Risks of aerobic exercise training

Previous studies have shown that aerobic exercise is safe for people to do in the first week after stroke. So far, 276 aerobic exercise bouts have been completed in the first week after stroke. 237 sessions (86%) involved walking, 32 sessions (12%) involved seated cycling or stepping, and 7 sessions (3%) involved sit-to-stand exercise. From these studies, we estimate that the risk of:

- Cardiovascular, neurological, or musculoskeletal complications is less than 1% (no adverse events have happened so far).
- Lower-limb pain is less than 2% (adverse events only happened in treadmill exercise).

- Getting a blister or superficial wound on the foot is 1.1% (adverse events only happened in treadmill exercise. Cycling places less pressure on the feet than walking).
- Dizziness is less than 7% (adverse events only happened in treadmill exercise which is possibly related to an upright head position. Cycling will be completed in bed with a reclined backrest).

[figure not shown]

Figure 4. Pie charts displaying the risk of adverse events related to aerobic exercise.

9. Investigations

Table 3. Schedule of investigations and outcome measures. Note: orange ticks indicate standard care.

	Study period																		
	Enrolment	Allocation	Post-allocation																
Post-stroke timeline	24-72 h (study starts)				≥48 h; 5-day intervention								+1 day	Follow-up					
	24-72 h (study starts)				≥48 h; 5-day intervention									+2 weeks	+3 months (study ends)				
Study timeline	t_{-1}	t_0		t_1		t_2		t_3		t_4		t_5		t_6		t_7		t_8	
	Group →	C	I	C	I	C	I	C	I	C	I	C	I	C	I	C	I	C	I
Eligibility screen	✓																		
Informed consent			✓	✓															
Age, sex, ethnicity			✓	✓															
Time since stroke (hours)	✓																		
Stroke severity (NIHSS)			✓	✓											✓	✓		✓	✓
Cardiovascular risk profile			✓	✓															
Group allocation			✓	✓															
Thigh muscle morphology (ultrasound)			✓	✓											✓	✓		✓	✓
Thigh accelerometer fitted			✓	✓															
Inpatient physical activity levels (thigh accelerometer)					✓	✓	✓	✓	✓	✓	✓	✓	✓	✓					

	Study period																	
	Enrolment	Allocation	Post-allocation															
Post-stroke timeline	24-72 h (study starts)				≥48 h; 5-day intervention								+1 day	Follow-up				
	+2 weeks			+3 months (study ends)														
Study timeline	t_{-1}	t_0		t_1	t_2		t_3	t_4		t_5	t_6		t_7	t_8				
	Group →	C	I	C	I	C	I	C	I	C	I	C	I	C	I	C	I	

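### Section 8.5.2 tells all patients that exercise has been shown to be safe, but the cited evidence documents no bout at NIHSS >15; section 8.3 also denies follow-up data that section 4.3 reports

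*Protocol*

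**What the plan says.** **Lay statement.** Section 8.5 covers what is to be communicated to patients. Its subsection 8.5.2 opens with "Previous studies have shown that aerobic exercise is safe for people to do in the first week after stroke". It then gives a total of 276 bouts, a split by mode of exercise and several risk percentages. The text qualifies some figures by mode but none by stroke severity.

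**Sources.** Section 4.3 describes the only training study, on treadmills: it "recruited 20 acute stroke patients (41.5 ± 14 h post-stroke; mild to no disability", and its authors concluded that "a 14.7% AE rate was acceptable (33 AEs in 224 exercise sessions". Section 8.3 adds three sources:
- a study of 6-minute tests ("median 4 days post-stroke; mild to moderate stroke; n=21")
- a graded exercise test study (n=28), with no severity given
- the team's own four pilot patients, with no severity given

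**Population.** Section 7.8 stratifies by NIHSS: "mild to moderate (0-15) and moderate to severe (>15". Table 4 justifies this as balancing the arms over the full range of severity. Sections 7.4 and 7.5 set no NIHSS limit.

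**Risk category.** Section 8.4.1 states: "Taking into account the absence of reported SAEs and our risk management procedures, we believe that this intervention is low risk". It then assigns type B because long-term follow-up is lacking. Severity is not mentioned.

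**Follow-up.** Section 4.3 says of the treadmill study that no SAEs "occurred in the 30-day follow-up period". Section 8.3 discusses the same study and then says that "none of the aforementioned studies reported follow-up safety outcomes".

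**The concern.** A patient deciding whether to take part should be told what the evidence covers. The lay text says safety has been shown and stops there. The protocol's own description of the sources shows that they are concentrated at the milder end, while the trial provides for patients above NIHSS 15. Such a patient would consent on a general assurance that the cited studies do not document for people like them.

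The rationale makes the gap easier to see. Section 4.4 says about 60% of patients cannot walk, or need help to walk, in the first week. Section 4.5 chooses power-assisted cycling to reach people with hemiplegia or hemiparesis. Yet 237 of the 276 bouts were walking.

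The follow-up sentence is a separate factual slip. Sections 4.3 and 8.3 make incompatible statements about the same study, in the part of the protocol an ethics committee would read for the safety case.

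**Working it through.** **1. Reproduce the protocol's total.** The inputs come from sections 4.3 and 8.3.

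| Source | Participants | Bouts | Severity as described |
|---|---|---|---|
| Treadmill training | 20 | 224 | mild to no disability |
| 6-minute walk or sit-to-stand | 21 | 13 + 7 = 20 | mild to moderate stroke |
| Graded exercise test | 28 | 28 | not stated |
| Team's pilot | 4 | 4 | not stated |
| Total | 73 | 276 | |

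- Bouts: 224 + 13 + 7 + 28 + 4 = 276, as stated. This leaves out the one walk test of 14 that was not completed; counting it gives 277.
- Modes: 224 + 13 = 237 walking, 28 + 4 = 32 seated cycling or stepping, 7 sit-to-stand, as in 8.5.2.
- Pooled AE rate: 33/276 = 12.0%, the stated mean. Dizziness: 19/276 = 6.9%, matching the stated figure of below 7%.

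The agreement on all three checks shows that this is the evidence the protocol used.

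**2. Split by stated severity.**
- Mild to no disability: 224/276 = 81.2% of bouts.
- Mild-to-moderate stroke: 20/276 = 7.2%.
- Together: 244/276 = 88.4%. With the uncompleted test counted, 245/277 = 88.4%.
- Severity not stated: 32/276 = 11.6%.
- Documented at NIHSS >15: 0.

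**3. The same split by participant.**
- Mild or mild-to-moderate: (20 + 21)/73 = 41/73 = 56.2%.
- Not stated: (28 + 4)/73 = 32/73 = 43.8%.

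The two units differ because 20 people supply 224 sessions. Both should be given.

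**4. Timing of the 28 graded tests.** Section 8.3 gives a median of day 9 (range 5 to 11) and says the acute share is not reported. At least half of these tests were therefore done on day 9 or later, so not all 28 are first-week evidence as 8.5.2 counts them.

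**5. Follow-up statements side by side.** Section 4.3 reports a 30-day follow-up without SAEs in the treadmill study. Section 8.3 cites that study first and then makes its flat statement about all the studies above. Both cannot be true. Section 8.4.1 refers only to long-term outcomes, so it can stand if 30 days is not regarded as long-term.

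**The case against.** **Entry is restricted.** Section 7.4 requires medical stability, enough comprehension and cognition to follow instructions and consent, and cycling ability in at least one leg. Section 7.5 lists further exclusions, 7.7 requires capacity and 8.1 bars absolute contraindications. NIHSS is scored after reperfusion therapy or at a similar time. This stands. A reader might infer that anyone able to cycle with one leg is enrolled, or that many patients above NIHSS 15 will enter. The protocol supports neither: such patients are not excluded, but their number is unknown.

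**Unstated is not mild.** A reader might infer from 88% that nearly everyone studied had a mild stroke. By participant the figure is 56%, and the remaining 32 people have no stated severity. They also supply the seated cycling or stepping bouts, the modes closest to the intervention. In addition, the treadmill study is described by disability, which is not the NIHSS scale. These points stand.

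**The lower stratum is partly covered.** The 21-patient study was in mild-to-moderate stroke and included seven non-ambulatory patients. It overlaps the 0-15 stratum, so a claim that everyone beyond mild stroke lacks evidence would go too far. The documented gap is at NIHSS >15.

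**Uncertainty is already acted on.** The protocol assigns type B, measures safety as an objective, and provides medical screening, monitoring and one-to-one supervision. The Study Doctor and an Investigator discuss risks with each patient. The information sheets are not shown and may be better qualified. This limits the consequence, but it does not make the sentence in 8.5.2 accurate.

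**The follow-up slip understates the evidence.** This is true, and no design element depends on it. It remains a contradiction.

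**Conclusion.** The point holds as a correction of wording. The safety statement in 8.5.2 is broader than the evidence the protocol describes: 88% of bouts (56% of participants) are from people with mild to no disability or mild-to-moderate stroke, severity is unstated for the rest, and none is documented at NIHSS >15. The flat follow-up sentence in 8.3 contradicts 4.3.

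A reader might go further and conclude that the exercise is unsafe in severe stroke, or that type B is the wrong category. The documents do not support that. They report no SAEs and simply do not document that group; the category already sits above standard care.

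The conclusion assumes that sections 4.3 and 8.3 describe the sources correctly, and that the information given to patients follows 8.5.2. If the sources of the 32 unstated bouts did include patients above NIHSS 15, the protocol should say so and the lay wording could be adjusted.

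**What to change.** - **Section 8.5.2 and the matching patient information:** replace the opening assurance. Say that no serious adverse events have been reported so far, that most of the evidence comes from people with mild or mild-to-moderate stroke, and that the cited studies do not document safety in more severe stroke (NIHSS >15). Section 8.5.1 already limits the claimed brain benefits to animal evidence, so a similar limit on safety fits the style.
- **Section 8.3:** reconcile the follow-up sentence with 4.3. One study reported 30 days without SAEs, and the cited studies give no long-term follow-up. The existing 3-month statement on the team's own pilot patients can stay.
- **Optional:** name the severity gap in 8.4.1, and list related AEs by baseline NIHSS. Neither changes the risk category or the design. With about 15 exercised patients (half of 30), such a list would be descriptive only.

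The cost is a few sentences in the protocol and the patient information, with whatever review the amended patient text needs. The evidence will read slightly less favourably on severity and slightly more favourably on follow-up.
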